Appendix 5. Physician Global Assessment of Fingernail Psoriasis (PGA-F)

Fingernail psoriasis will be assessed using a 5-point PGA scale. The assessor should select the category that best represents the condition of all of the fingernails.

0 = Clear	Normal fingernails with no signs of psoriasis in the nail plates or nail beds
1 = Minimal	Just perceptible nail plate pitting, crumbling, onycholysis, oil drop discoloration, and/or nail bed hyperkeratosis
2 = Mild	Mild nail plate pitting, crumbling, onycholysis, oil drop discoloration, and/or nail bed hyperkeratosis
3 = Moderate	Moderate nail plate pitting, crumbling, onycholysis, oil drop discoloration, and/or nail bed hyperkeratosis
4 = Severe	Severe nail plate pitting, crumbling, onycholysis, oil drop discoloration, and/or nail bed hyperkeratosis

Appendix 6. Body Surface Area (BSA)

The body surface area (BSA) assessment estimates the extent of disease or skin involvement with respect to atopic dermatitis (AD) and is expressed as a percentage of total body surface.

Determine BSA using the patient's palm = 1% BSA rule.

The patient's palm is measured from the wrist to the proximal interphalangeal and thumb.

Estimate the number of palms it takes to cover the affected AD area. Add up the number of palms to give a total estimate of the area covered in AD.

Additional rules:

- 1. When many small lesions are present, try to put several together to make one patient palm.
- 2. Only include the edge of current lesions, not areas that have cleared.
- 3. Double check to see if area derived matches eyeball method.

Appendix 7. Psoriasis Symptom Scale (PSS)

- 1. How severe was your pain from your psoriasis during the past 24 hours?
 - None
 - Mild
 - Moderate
 - Severe
 - Very severe
- 2. How severe was the redness from your psoriasis during the past 24 hours?
 - None
 - Mild
 - Moderate
 - Severe
 - Very severe
- 3. How severe was your itching from your psoriasis during the past 24 hours?
 - None
 - Mild
 - Moderate
 - Severe
 - Very severe
- 4. How severe was your burning from your psoriasis during the past 24 hours?
 - None
 - Mild
 - Moderate
 - Severe
 - Very severe

Appendix 8. Dermatology Life Quality Index (DLQI)

The aim of this questionnaire is to measure how much your skin problem has affected your life OVER THE LAST WEEK. Please tick (X) one box for each question.

1. Over the last week, how itchy , sore , painful , or stinging has your skin been?	Very much □ A lot □ A little □ Not at all □
2. Over the last week, how embarrassed or self-conscious have you been because of your skin?	Very much □ A lot □ A little □ Not at all □ Not relevant □
3. Over the last week, how much has your skin interfered with you going shopping or looking after your home or garden ?	Very much □ A lot □ A little □ Not at all □ Not relevant □
4. Over the last week, how much has your skin influenced the clothes you wear?	Very much □ A lot □ A little □ Not at all □ Not relevant □
5. Over the last week, how much has your skin affected any social or leisure activities?	Very much □ A lot □ A little □ Not at all □ Not relevant □
6. Over the last week, how much has your skin made it difficult for you to do any sport ?	Very much □ A lot □ A little □ Not at all □ Not relevant □
7. Over the last week, has your skin prevented you from working or studying? If "No", over the last week how much has your skin been a problem at work or studying?	Yes
8. Over the last week, how much has your skin created problems with your partner or any of your close friends or relatives ?	Very much □ A lot □ A little □ Not at all □ Not relevant □
9. Over the last week, how much has your skin caused any sexual difficulties ?	Very much □ A lot □ A little □ Not at all □ Not relevant □

10. Over the last week, how much of a problem has	Very mucl	1 🗆		
the treatment for your skin been, for example by	A lot			
making your home messy, or taking up time?	A little			
	Not at all		Not relevant	

☐ Please check you have answered EVERY question. Thank you.

Appendix 9. The Hospital Anxiety and Depression Scale (HADS)

Hospital Anxiety and Depression Scale (HADS)

Tick the box beside the reply that is closest to how you have been feeling in the past week.

D	A	Don't take too long over you	D	A	Walter Committee
_	100	I feel tense or 'wound up':			I feel as if I am slowed down:
	3	Most of the time	3		Nearly all the time
	2	A lot of the time	2		Very often
	1	From time to time, occasionally	1	12	Sometimes
	0	Not at all	0		Not at all
	100	Leof Settings	72	8	1
		I still enjoy the things I used to enjoy:			I get a sort of frightened feeling like 'butterflies' in the stomach:
0		Definitely as much		0	Not at all
1		Not quite so much		1	Occasionally
2		Only a little		2	Quite Often
3		Hardly at all		3	Very Often
3		I get a sort of frightened feeling as if something awful is about to happen:	S		I have lost interest in my appearance:
3	3	Very definitely and quite badly	3	86	Definitely
	2	Yes, but not too badly	2		I don't take as much care as I should
	1	A little, but it doesn't worry me	1	8	I may not take quite as much care
_	0	Not at all	0		I take just as much care as ever
		I can laugh and see the funny side of things:		0.	I feel restless as I have to be on the move:
0		As much as I always could		3	Very much indeed
1		Not quite so much now		2	Quite a lot
2		Definitely not so much now		1	Not very much
3		Not at all		0	Not at all
		Worrying thoughts go through my mind:			I look forward with enjoyment to things:
	3	A great deal of the time	0		As much as I ever did
	2	A lot of the time	1	2	Rather less than I used to
	1	From time to time, but not too often	2		Definitely less than I used to
	0	Only occasionally	3		Hardly at all
	10	I feel cheerful:		100	I get sudden feelings of panic:
3		Not at all		3	Very often indeed
2	1	Not often		2	Quite often
1		Sometimes		1	Not very often
0	-	Most of the time		0	Not at all
		I can sit at ease and feel relaxed:		0	I can enjoy a good book or radio or TV program:
	0	Definitely	0		Often
	1	Usually	1		Sometimes
	2	Not Often	2		Not often
	3	Not at all	3	6	Very seldom

Please check you have answered all the questions

Scorin	ng:		
Total	score: Depression (D)	Anxiety (A)	
0-7	= Normal		
8-10	= Borderline abnormal (border	line case)	
11-21	= Abnormal (case)		

Appendix 10. The Columbia-Suicide Severity Rating Scale (C-SSRS)

For Screening

	Past	Year
Ask questions that are bolded and underlined .	YES	NO
Ask Questions 1 and 2	ı.	
1) Have you wished you were dead or wished you could go to sleep and not wake up?		
2) Have you actually had any thoughts of killing yourself?		
If YES to 2, ask questions 3, 4, 5, and 6. If NO to 2, go directly to question 6.		
3) Have you been thinking about how you might do this? E.g., "I thought about taking an overdose, but I never made a specific plan as to when where or how I would actually do itand I would never go through with it."		
4) Have you had these thoughts and had some intention of acting on them? As opposed to "I have the thoughts, but I definitely will not do anything about them."		
5) Have you started to work out or worked out the details of how to kill yourself? Did you intend to carry out this plan?		
6) Have you ever done anything, started to do anything, or prepared to do anything to end your life? Examples: Collected pills, obtained a gun, gave away valuables, wrote a will or suicide note, took out pills but did not swallow any, held a gun but changed your mind or it was grabbed from your hand, went to the roof but did not jump; or actually took pills, tried to shoot yourself, cut yourself, tried to hang yourself, etc. If YES, ask: Was this within the past 3 months?		

For Study

SUICIDAL IDEATION	
Ask questions 1 and 2. If both are negative, proceed to "Suicidal Behavior" section. If the answer to question 2 is "yes", ask questions 3, 4 and 5. If the answer to question 1 and/or 2 is "yes", complete "Intensity of Ideation" section below.	Since Last Visit
1. Wish to be Dead Subject endorses thoughts about a wish to be dead or not alive anymore or wish to fall asleep and not wake up. Have you wished you were dead or wished you could go to sleep and not wake up?	Yes □ No □
If yes, describe: 2. Nonspecific Active Suicidal Thoughts General nonspecific thoughts of wanting to end one's life/die by suicide (e.g., "I've thought about killing myself") without thoughts of ways to kill oneself/associated methods, intent, or plan during the assessment period. Have you actually had any thoughts of killing yourself? If yes, describe:	Yes □ No □
3. Active Suicidal Ideation with Any Methods (Not Plan) without Intent to Act Subject endorses thoughts of suicide and has thought of at least one method during the assessment period. This is different than a specific plan with time, place or method details worked out (e.g., thought of method to kill self but not a specific plan). Includes person	Yes □ No □

who would say, "I thought about taking an overdose, but I never made a specific plan as to when, where or how I would actually do itand I would never go through with it." Have you been thinking about how you might do this?	
If yes, describe:	
4. Active Suicidal Ideation with Some Intent to Act, without Specific Plan Active suicidal thoughts of killing oneself and subject reports having some intent to act on such thoughts, as opposed to "I have the thoughts, but I definitely will not do anything about them." Have you had these thoughts and had some intention of acting on them?	Yes □ No □
If yes, describe:	
5. Active Suicidal Ideation with Specific Plan and Intent Thoughts of killing oneself with details of plan fully or partially worked out and subject has some intent to carry it out. Have you started to work out or worked out the details of how to kill yourself? Did you intend to carry out this plan?	Yes □ No □
If yes, describe:	
INTENSITY OF IDEATION	
The following features should be rated with respect to the most severe type of ideation (i.e., 1-5 from above, with 1 being the least severe and 5 being the most severe). Ask about time he/she was feeling the most suicidal.	
Lifetime - Most Severe IdeationType # (1-5)	Most Severe
Description of Ideation	Severe
Recent - Most Severe Ideation:Type # (1-5)	
Description of Ideation	
Frequency	
How many times have you had these thoughts? (1) Less than once a week (2) Once a week (3) 2-5 times in week (4) Daily or almost daily	
(5) Many times each day	
Duration	
When you have the thoughts how long do, they last?	
(1) Fleeting - few seconds or minutes (2) Less than 1 hour/some of the time	
(3) 1-4 hours/a lot of time	
(4) 4-8 hours/most of day	
(5) More than 8 hours/persistent or continuous	
Controllability	
Could/can you stop thinking about killing yourself or wanting to die if you want to?	
(1) Easily able to control thoughts(2) Can control thoughts with little difficulty	
(3) Can control thoughts with intie difficulty	
(4) Can control thoughts with a lot of difficulty	
(5) Unable to control thoughts	
(0) Does not attempt to control thoughts	
Deterrents	
Are there things - anyone or anything (e.g., family, religion, pain of death) - that stopped you from wanting to die or acting on thoughts of suicide?	

(1) Deterrents definitely stopped you from attempting suicide	
(2) Deterrents probably stopped you	
(3) Uncertain that deterrents stopped you(4) Deterrents most likely did not stop you	
(5) Deterrents definitely did not stop you	
(3) Determine definitely did not stop you (0) Does not apply	
Reasons for Ideation	
What sort of reasons did you have for thinking about wanting to die or killing	
yourself? Was it to end the pain or stop the way you were feeling (in other words)	VOII
couldn't go on living with this pain or how you were feeling) or was it to get attent	
revenge, or a reaction from others? Or both?	1011,
(1) Completely to get attention, revenge, or a reaction from others	
(2) Mostly to get attention, revenge, or a reaction from others	
(3) Equally to get attention, revenge, or a reaction from others and to end/stop the pain	
(4) Mostly to end or stop the pain (you could not go on living with the pain or how you	
were feeling)	
(5) Completely to end or stop the pain (you could not go on living with the pain or how	
you were feeling)	
(0) Does not apply	
SUICIDAL BEHAVIOR	
(Check all that apply, so long as these are separate events; must ask about all types)	Since Last Visit
Actual Attempt:	Yes No
A potentially self-injurious act committed with at least some wish to die, as a result	
of act. Behavior was in part thought of as method to kill oneself. Intent does not	
have to be 100%. If there is any intent/desire to die associated with the act, then it	
can be considered an actual suicide attempt. There does not have to be any injury or	
harm , just the potential for injury or harm. If person pulls trigger while gun is in	
mouth, but gun is broken so no injury results, this is considered an attempt.	
Inferring Intent: Even if an individual denies intent/wish to die, it may be inferred	
clinically from the behavior or circumstances. For example, a highly lethal act that is	
clearly not an accident so no other intent, but suicide can be inferred (e.g., gunshot to	Total # of
head, jumping from window of a high floor/story). Also, if someone denies intent to	Attempts
die, but they thought that what they did could be lethal, intent may be inferred.	
Have you made a suicide attempt?	
Have you done anything to harm yourself?	
Have you done anything dangerous where you could have died?	
What did you do?	
Did youas a way to end your life? Did you want to die (even a little) when you?	
Were you trying to end your life when you?	
Or did you think it was possible you could have died from?	
Or did you do it purely for other reasons / without ANY intention of killing yourself	
(like to relieve stress, feel better,	
get sympathy, or get something else to happen)? (Self-Injurious Behavior without	
suicidal intent)	
If yes, describe:	
Has subject engaged in Nonsuicidal Self-Injurious Behavior?	
Interrupted Attempt:	Yes No
When the person is interrupted (by an outside circumstance) from starting the	
potentially self-injurious act (if not for that, actual attempt would have occurred).	
Overdose: Person has pills in hand but is stopped from ingesting. Once they ingest	
any pills, this becomes an attempt rather than an interrupted attempt. Shooting:	
Person has gun pointed toward self, gun is taken away by someone else, or is	Total # of interrupted
somehow prevented from pulling trigger. Once they pull the trigger, even if the gun	

fails to fire, it is an attempt. Jumping: Person is poised to jump, is grabbed, and	
taken down from ledge. Hanging: Person has noose around neck but has not yet	
started to hang - is stopped from doing so.	
Has there been a time when you started to do something to end your life but	
someone or something stopped you before you actually did anything?	
If yes, describe:	
Aborted or Self-Interrupted Attempt:	Yes No
When person begins to take steps toward making a suicide attempt but stops	
themselves before they actually have engaged in any self-destructive behavior.	
Examples are similar to interrupted attempts, except that the individual stops	Total # of
him/herself, instead of being stopped by something else.	aborted or self-
Has there been a time when you started to do something to try to end your life, but	interrupted
you stopped yourself before you actually did anything?	
If yes, describe:	
Preparatory Acts or Behavior:	Yes No
Acts or preparation towards imminently making a suicide attempt. This can include anything beyond a verbalization or thought, such as assembling a specific method	
(e.g., buying pills, purchasing a gun) or preparing for one's death by suicide (e.g.,	Total # of preparatory
giving things away, writing a suicide note).	acts
Have you taken any steps towards making a suicide attempt or preparing to kill	
yourself (such as collecting pills, getting a gun, giving valuables away or writing a	
suicide note)?	
If yes, describe:	
M	41 .1 A44 4 D. 4
	thal Attempt Date:
Actual Lethality/Medical Damage:	F4 C1-
0. No physical damage or very minor physical damage (e.g., surface scratches).	Enter Code
1. Minor physical damage (e.g., lethargic speech; first-degree burns; mild bleeding; sprains).	
2. Moderate physical damage; medical attention needed (e.g., conscious but sleepy,	
somewhat responsive; second-degree burns; bleeding of major vessel).	
3. Moderately severe physical damage; medical hospitalization and likely intensive	
care required (eg, comatose with reflexes intact; third-degree burns less than	
20% of body; extensive blood loss but can recover; major fractures).	
4. Severe physical damage; medical hospitalization with intensive care required (eg,	
comatose without reflexes; third-degree burns over 20% of body; extensive blood	
loss with unstable vital signs; major damage to a vital area).	
loss with unstable vital signs; major damage to a vital area). 5. Death	
loss with unstable vital signs; major damage to a vital area). 5. Death Potential Lethality: Only Answer if Actual Lethality = 0	
loss with unstable vital signs; major damage to a vital area). 5. Death Potential Lethality: Only Answer if Actual Lethality = 0 Likely lethality of actual attempt if no medical damage (the following examples,	Enter Code
loss with unstable vital signs; major damage to a vital area). 5. Death Potential Lethality: Only Answer if Actual Lethality = 0 Likely lethality of actual attempt if no medical damage (the following examples, while having no actual medical damage, had potential for very serious lethality: put	Enter Code
loss with unstable vital signs; major damage to a vital area). 5. Death Potential Lethality: Only Answer if Actual Lethality = 0 Likely lethality of actual attempt if no medical damage (the following examples, while having no actual medical damage, had potential for very serious lethality: put gun in mouth and pulled the trigger but gun fails to fire so no medical damage; laying	Enter Code
loss with unstable vital signs; major damage to a vital area). 5. Death Potential Lethality: Only Answer if Actual Lethality = 0 Likely lethality of actual attempt if no medical damage (the following examples, while having no actual medical damage, had potential for very serious lethality: put	Enter Code
loss with unstable vital signs; major damage to a vital area). 5. Death Potential Lethality: Only Answer if Actual Lethality = 0 Likely lethality of actual attempt if no medical damage (the following examples, while having no actual medical damage, had potential for very serious lethality: put gun in mouth and pulled the trigger but gun fails to fire so no medical damage; laying on train tracks with oncoming train but pulled away before run over).	Enter Code
loss with unstable vital signs; major damage to a vital area). 5. Death Potential Lethality: Only Answer if Actual Lethality = 0 Likely lethality of actual attempt if no medical damage (the following examples, while having no actual medical damage, had potential for very serious lethality: put gun in mouth and pulled the trigger but gun fails to fire so no medical damage; laying	Enter Code

Posner K, Brown GK, Stanley B, Brent DA, Yershova KV, Oquendo MA, Currier GW, Melvin GA, Greenhill L, Shen S, Mann JJ. The Columbia-Suicide Severity Rating Scale: initial validity

and internal consistency findings from 3 multisite studies with adolescents and adults. Am J Psychiatry. 2011 Dec;168(12):1266-77.

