5.3. Clinical Risks/Benefits

Despite the positive and encouraging efficacy results of the Phase 2a study of the immediate-release tablets of orismilast, this formulation presented an undesirable safety profile with 50% of patients prematurely discontinuing because of GI effects. To improve the GI tolerance, several formulations were tested in an extensive Phase 1 clinical program, leading to the selection of a modified-release formulation with notably better GI tolerance in healthy volunteers. The modified-release formula is expected to mitigate potential GI effects previously observed in psoriasis patients with the immediate-release tablets while maintaining the efficacy previously observed. The titration dosing schedule at the initiation of study treatment will help to reduce the incidence and severity of GI side effects that tend to occur primarily when starting therapy. The improved safety profile of the modified-release formulation is expected to make the therapeutic window of orismilast wider this allowing to achieve dosing levels with adequate efficacy and good tolerability.

Occurrence and severity of GI disorders will be promptly identified by monitoring the subjects for any signs of abdominal discomfort, abdominal distension, abdominal pain, nausea, vomiting, loss of appetite, and diarrhea. Depending on their severity, these AEs may qualify as an adverse event of special interest (AESI). Based on the occurrence of GI or other AEs considered having a causal relationship with study treatment, the Investigator might consider decreasing the daily dosing regimen or stopping the treatment for a few days, until recovery. Besides the above, all subjects will be monitored for any cardiovascular manifestations using vital signs and 12-lead ECG at each visit. Drug class potential effects such as weight loss and major depression will be monitored during the study. Subjects with major depression, presenting major psychiatric disorders or at risk for suicide will be excluded from enrollment, and suicidal ideation and depressive symptoms will be assessed in the course of the study by Columbia-Suicide Severity Rating Scale (C-SSRS) and Hospital Anxiety and Depression Scale (HADS), respectively. Patients will be informed of the potential increased risk of depression or suicidal thoughts of this class of drugs; and recommended to promptly contact their study doctor in case of such event.

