6.2.2.3. Safety Endpoints

- The occurrence, severity, and seriousness of treatment-emergent adverse events (TEAEs) reported over the 16-week Treatment Period and the 4-week Follow-up Period.
- Changes from Baseline in physical examination; vital sign measurements (body temperature, respiration rate, heart rate, and systolic and diastolic blood pressure measurements); and body weight over the 16-week Treatment Period and the 4-week Follow-up Period.
- Changes from Baseline in ECG findings over the 16-week Treatment Period and the 4-week Follow-up Period.
- Changes from Baseline in safety laboratory values (hematology, serum chemistry, and urinalysis) over the 16-week Treatment Period and the 4-week Follow-up Period.
- HADS at each visit except Screening, Week 1 and Week 2.
- C-SSRS at each visit except Weeks 1 and 2.

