7. INVESTIGATIONAL PLAN

7.1. Description of Overall Study Design and Plan

This multicenter, randomized, double-blind, placebo-controlled, parallel-group, Phase 2b doseranging study is designed to assess the efficacy and safety of modified-release orismilast compared with placebo in adult patients with moderate-to-severe plaque-type psoriasis. Efficacy and safety outcomes will be evaluated to select an appropriate orismilast dose for subsequent Phase 3 studies. The study will be conducted in approximately 40 centers in Europe and North America.

After a Screening visit up to 28 days before Baseline, approximately 200 patients will be assigned randomly in a 1:1:1:1 ratio to receive 1 of the 3 orismilast doses (20 mg, 30 mg, or 40 mg) or placebo twice daily (BID) for 16 weeks, with a 4-week Follow-up visit. Administration will begin at Baseline with a dose titration period. The maximum duration of study participation is approximately 24 weeks.

Patients will be seen at the site on Screening, Baseline (Day 1), and Weeks 1, 2, 4, 8, 12, 16 (End-of-Treatment [EOT] visit), and 20 (Follow-up visit, 4 weeks after treatment completion or discontinuation). Visits at Weeks 1 and 2 could be conducted via a telemedicine procedure at Investigator's discretion.

N=50 Orismilast 20 mg BID (2 x 10 mg tablets) N=50 Orismilast 30 mg BID Screening (1 x 30 mg tablet and 1 x placebo tablet*) N=50 Orismilast 40 mg BID (1 x 10 mg tablet and 1 x 30 mg tablet) N=50 Placebo BID (2 x placebo tablets)* **Treatment Period** Follow up Randomization End of Period (16 weeks) Treatment (1:1:1:1)

Figure 1. Study Design

Abbreviation: BID, twice a day

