12.8. The Columbia-Suicide Severity Rating Scale

The C-SSRS, Investigator administered version, was designed to provide a prospective, standardized measure of suicidality. The scale allows clinicians and researchers alike to assess the severity and lethality of suicidal behaviors and ideations and can be used to monitor treatment outcomes and establish suicide risk in a variety of research and clinical settings. Requiring approximately 5 min for completion, the C-SSRS is administered in the form of a clinical interview.

This C-SSRS is available in 2 versions: 1 for use at Screening referring to the past year and 1 for use throughout the rest of the study referring to the time since the prior visit.

If at Screening or Baseline there are "yes" answers on items 4 or 5 in the past year, the patient will not be included in the study.

Any subject with a positive response on the C-SSRS (answers "yes" to questions 1-5) should be referred to a mental health specialist (psychiatrist or clinical psychologist) for further evaluation, and the study medication should be paused. After a mental health specialist evaluation, the final decision on restarting or permanently discontinuing study treatment will be at the discretion of the Investigator in consultation with the mental health specialist. These cases should be reported as an AESI. Refer to Section 0.

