#### **12.7. The Columbia-Suicide Severity Rating Scale**

The C-SSRS, investigator administered version, was designed to provide a prospective, standardized measure of suicidality. The scale allows clinicians and researchers alike to assess the severity and

*This document is confidential.*

lethality of suicidal behaviors and ideations and can be used to monitor treatment outcomes and establish suicide risk in a variety of research and clinical settings. Requiring approximately 5 min for completion, the C-SSRS is administered in the form of a clinical interview. This C-SSRS is available in 2 versions: 1 for use at screening referring to the past year and 1 for use throughout the rest of the study referring to the time since the prior visit.

C-SSRS will be collected at different time points as per the SoA in Protocol Section 10.

The C-SSRS categories have been re-ordered from the actual scale to facilitate the definitions of the endpoints, and to enable clarity in the presentation of the results: category 1 – Wish to be Dead, category 2 – Non-specific Active Suicidal Thoughts, category 3 – Active Suicidal Ideation with Any Methods (Not Plan) without Intent to Act, category 4 – Active Suicidal Ideation with Some Intent to Act, without Specific Plan, category 5 – Active Suicidal Ideation with Specific Plan and Intent, category 6 – Preparatory Acts or Behavior, category 7 – Aborted Attempt, category 8 – Interrupted Attempt, category 9 – Actual Attempt (non-fatal), category 10 – Completed Suicide.

Suicidal ideation is defined as a “yes” answer at any time during treatment to any one of the five suicidal ideation questions (Categories 1-5) on the C-SSRS. Suicidal behavior is defined as a “yes” answer at any time during treatment to any one of the five suicidal behavior questions (Categories 6-10) on the C-SSRS. Suicidal ideation or behavior is defined as a “yes” answer at any time during treatment to any one of the ten suicidal ideation and behavior questions (Categories 1-10) on the C-SSRS.

A summary table presenting number of patients with suicidal ideation, suicidal behavior, and self-injurious behavior without suicidal intent will be generated, as well as a shift table to demonstrate changes in C-SSRS suicidal ideation scores from baseline to all post-baseline visits by treatment. Patients with suicidal ideation, suicidal behavior, or self-injurious behavior without suicidal intent based on the C-SSRS will be listed.

This document is confidential.

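### As worded, the Week 4 C-SSRS looks back only to the Week 2 visit, so about the first 14 of 112 treatment days fall in no C-SSRS recall window

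*Protocol*

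**What the plan says.** **Recall period.** Protocol 12.8 describes two versions of the scale. One is for Screening and covers the past year; the other is "1 for use throughout the rest of the study referring to the time since the prior visit". SAP 12.7 repeats this. The on-study form in Appendix 10 heads both its ideation and its behaviour sections "Since Last Visit".

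**Schedule.** Protocol 6.2.2.3 lists "C-SSRS at each visit except Weeks 1 and 2". SAP 5.5 and Table 4 agree: Screening, Day 1, and Weeks 4, 8, 12, 16 and 20.

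**Weeks 1 and 2 are visits.** Protocol 7.1 states: "Patients will be seen at the site on Screening, Baseline (Day 1), and Weeks 1, 2, 4, 8, 12, 16". It adds: "Visits at Weeks 1 and 2 could be conducted via a telemedicine procedure at Investigator's discretion". In Table 4 both weeks have their own column, with adverse event review, medication review and a compliance check.

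**Reporting.** SAP 12.7 counts suicidal ideation as a yes "answer at any time during treatment to any one of the five suicidal ideation questions", and treats suicidal behaviour in the same way. The counts go to Table 14.3.4.4.5 and the shifts to Table 14.3.4.4.6.

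**Importance.** Protocol 5.3 says that patients will be told of the "potential increased risk of depression or suicidal thoughts of this class of drugs".

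**The concern.** The recall rule counts back to the preceding visit, whether or not the C-SSRS was given there. That works only if every visit includes a C-SSRS, and Weeks 1 and 2 do not. The Week 4 interview therefore appears to start its look-back at Week 2, and the time from first dose to Week 2 belongs to no interview.

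Two things are at stake. First, the SAP table claims coverage of the whole treatment period, which the instrument as worded does not give. A patient with suicidal thoughts on Day 5 that had resolved by Week 2 could be recorded as negative at Week 4, and so in the C-SSRS table and the shift table. Second, Protocol 12.8 ties referral, pausing of study medication and AESI reporting to a positive C-SSRS. For this interval the scale as worded would not set those steps in motion.

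The uncovered time is first exposure and up-titration, in a trial whose secondary objective is to choose a dose on benefit and risk. Suicidality is both a safety endpoint and a named class risk.

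**Working it through.** The plan states no figure on this point, so there is none to reproduce. The check lays the visit schedule against the recall rule.

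**Inputs**
- Visit days, counted as days since first dose (the SAP 7.4 convention): Week 4 = 28, Week 8 = 56, Week 12 = 84, Week 16 = 112. By the same count, Week 1 = 7, Week 2 = 14, Week 20 = 140.
- Week 2 window: ±1 day (Table 4).
- First dose: evening of Day 1 (Protocol 9.1), after the Baseline C-SSRS.
- Titration: at most two weeks, Days 1 to 14 (Protocol 9.3.1 and Table 2; SAP 4.1 also says up to 14 days).

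**Windows under each reading**

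| C-SSRS visit | Preceding visit | Window as written (days) | Window from last C-SSRS (days) |
|---|---|---|---|
| Week 4 | Week 2 | 14 to 28 | 0 to 28 |
| Week 8 | Week 4 | 28 to 56 | 28 to 56 |
| Week 12 | Week 8 | 56 to 84 | 56 to 84 |
| Week 16 | Week 12 | 84 to 112 | 84 to 112 |
| Week 20 | Week 16 | 112 to 140 | 112 to 140 |

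From Week 4 onward each scheduled visit has a C-SSRS, so only the first interval is broken.

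**Size of the gap as written**
- Uncovered days = Week 2 day − 0 = 14. Share of treatment = 14/112 = 12.5%.
- Week 2 one day early: 13/112 = 11.6%. One day late: 15/112 = 13.4%.
- Share of the first four weeks: 14/28 = 50%.
- Titration days uncovered: 14 of 14, or 13 of 14 if Week 2 is held a day early.
- If Week 2 is missed and Week 1 is held, the look-back starts at Week 1: 7/112 = 6.3%. If neither is held, it reaches Baseline and there is no gap.

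**Size of the gap if recall runs from the last C-SSRS:** 0 of 112 days.

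**Can another instrument fill it?** The HADS cannot. Its items in Appendix 9 ask nothing about suicide, and the patient marks the reply "closest to how you have been feeling in the past week". Table 4 and Protocol 6.2.2.3 first repeat it at Week 4. The protocol synopsis and SAP 5.5 exclude only Week 2, which would imply a Week 1 HADS. Those passages need reconciling, but neither schedule closes the gap.

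**Does the form's *Lifetime* line fill it?** No. It sits in the intensity section, which is completed only after a yes to question 1 or 2 for the stated period.

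**The case against.** The best counter-argument is that the gap depends on taking *visit* literally. Items 2 and 3 of the form refer to an assessment period, which fits the interval between two C-SSRS interviews. The SAP's whole-treatment definition suggests that continuous coverage was intended, and on that reading nothing is uncovered. The spoken questions carry no date limit, so a patient might mention a Day 5 episode at Week 4 anyway. Section 18 of the protocol says the appendix forms are samples, and the rater and eCRF instructions are not in the documents.

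Part of this stands. The gap is a consequence of the wording, and raters may not all apply it. But neither document tells the rater to go back to the last C-SSRS. The sample-form note does not help either, because the body text of Protocol 12.8 and of SAP 12.7 carries the same rule. If some raters follow the text and others the likely intent, sites will use different recall periods.

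A reader might infer that suicidality goes unmonitored in the first two weeks. The documents do not support that. Adverse events are reviewed at Weeks 1 and 2. Any adverse event of suicidal ideation or behaviour is an AESI reportable within 24 hours, whatever the C-SSRS shows (Protocol 12.9.2), and AESIs have their own table (14.3.1.17). Protocol 5.3 also has patients advised to contact the study doctor promptly. What is missing in those weeks is the structured interview.

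**Conclusion.** The point holds as an ascertainment gap created by a stated rule. Followed as written, the C-SSRS covers about 98 of 112 treatment days (112 − 14), while SAP 12.7 reports its results as if all 112 were covered. An episode is at risk of being lost from the C-SSRS tables only if it starts after the first dose, has resolved by the Week 2 visit, and the rater applies the recall period literally. Episodes that last beyond Week 2 are caught even as worded.

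A reader might infer that 12.5% of the time means about 1 in 8 episodes missed. The documents do not support that step. It would need every episode to be short and onset to be even over treatment, and no onset or duration data are given. Multiplying 14 days by the number of patients would likewise measure exposure time, not missed events. The number of missed episodes cannot be estimated.

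The result assumes that Weeks 1 and 2 are both held, in person or remotely, and that treatment lasts the planned 112 days. The description of the gap as the titration period follows the protocol's two weeks. In Table 2 the 20 mg and 30 mg arms reach their full regimen on Day 8 and Day 9, and only the 40 mg arm titrates through Day 14. The SAP 12.1 adverse event tables call the titration period the initial 3 weeks, which must be reconciled with SAP 4.1 and the protocol.

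The correction is worth making because the endpoint is a named safety concern and the remedy costs almost nothing.

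**What to change.** Add one sentence to Protocol 12.8, to SAP 12.7 and to the rater and eCRF guidance, for example: *The recall period of the on-study C-SSRS runs from the last completed C-SSRS; at Week 4 this is the Baseline (Day 1) assessment.* This also covers a missed C-SSRS or an unscheduled visit without one.

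Leave the standard form text unchanged, including its *Lifetime* line. The guidance is enough, and a standardised instrument should not be reworded for this. No visit, procedure or clinical rule changes.

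The cost is the wording itself and a note to raters. The one downside is that Week 4 recall lengthens from about 2 weeks (28 − 14 = 14 days) to about 4 weeks (28 days), the same as at each later scheduled visit.
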